CBZ is absorbed slowly after oral administration with peak concentrations reached within 4-8 hours. This is mostly due to the time it takes for dissolution of CBZ tablets. The bioavailability is estimated at 75-85% and variably affected by food intake (19). CBZ is distributed throughout the body and ~75% is bound to albumin. It passes the blood-brain barrier, placenta and penetrates breast milk.

Safety

CBZ is a very safe drug with minimal side effects noted after extensive use (15). Side effects have led to reduction of dosage in only 3% of patients receiving the drug and to discontinuation of the drug in another 3%. Dose dependent side effects include drowsiness, sedation, vertigo and ophthalmoplegia. These tend to occur early in treatment and dissipate with chronic treatment in an overwhelming number of cases. Use of a dose escalation schedule also reduces the incidence of these side effects. Hyponatremia has been noted, especially in elderly patients. It is usually mild and asymptomatic. It may lower plasma concentrations of thyroid binding globulin, bound and unbound T4 and T3 but clinical hypothyroidism is rare. CBZ treatment may be associated with elevated serum transaminase levels in 5-10% of cases. In the vast majority of these cases CBZ can be continued without dose reduction. On rare occasions when evidence for hepatic dysfunction develops, CBZ must be discontinued.

Severe idiosyncratic reactions are rare. Hematological toxicity with aplastic anemia, agranulocytosis and or thrombocytopenia has been estimated to occur in less than 1 in 50,000 individuals treated with CBZ. A dose-dependent reduction in neutrophil count occurs in 10-20% of patients. However, the neutrophil count rarely goes below 1,200 per mm³ and CBZ administration has not been associated with an increase in infections. Allergic rash occurs in 4 to 10% of patients and is the most common reason for intolerance to CBZ. Allergic reactions with fever, renal and hepatic toxicity are very rare.

A Preliminary Study of the Efficacy and Safety of Carbamazepine in Severe Liver Disease Due to Alpha-1 Antitrypsin Deficiency

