During therapy, study subjects will be seen on a regular basis to assess their clinical status and to obtain standard biochemical measures of liver and renal function, cell counts, etc. Visits will also include a full history and physical examination. Specific assessments and queries will be made for any signs or symptoms of liver disease. Child-Pugh (CP) score and MELD score will be calculated at each study visit. Other than blood collection during study visits, no additional invasive testing is proposed until the week 52b visit when a repeat liver biopsy and HVPg will be obtained. The procedure for the liver biopsy and HVPg will be identical to the procedure used in the screening visit. Data will be collected from procedures undertaken as part of clinical follow up (e.g. endoscopy reports, imaging studies, etc.).

If the study subject undergoes liver transplantation during the study period, samples will be obtained at the time of surgery to provide follow up data. If a subject dies during the study period and the family consents to an autopsy, samples of liver tissue will be obtained at autopsy to provide follow up data. In these cases, follow up HVPg measurements will not be available.

Potential for suicide attempts will be monitored with the Columbia Suicide Severity Rating Scale (C-SSRS) at study visits the week of enrollment through week 52a. It is a semi-structured, clinician-administered instrument to track severity of both suicidal behavior and ideation. This measure is reliable and valid and has been used in previous clinical trials (44, 45). Patients will be withdrawn from the trial if the C-SSRS identifies suicidal ideation or behavior and then the patient will then be referred for mental health evaluation and treatment.

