Study visits will be scheduled at weeks 4 (+/- 1 week), 8 (+/- 2 weeks), 18 (+/- 2 weeks), 36 (+/- 2 weeks), and 52a (+ 3 weeks) for a history and physical examination, assessment for depression and suicide behavior, biochemistry measures, and measurement of the blood level of the CBZ. Blood will also be collected at the time of enrollment and at week 52 visit for Fibrotest analysis. All female subjects of child-bearing age will undergo a urine pregnancy test on visit S2, enrollment, and at each follow up visit during the trial. The effect of CBZ treatment will also be assessed by a novel investigative test, a hepatic biomarker assay using samples that are obtained pre- and post-treatment as well as once during treatment. Study subjects may undergo MRI using Elastography within the first six months of study enrollment and at week 52 visit.

Additional visits may be scheduled, at the discretion of the Investigator, to ensure the safety and well-being of subjects. These will include a history, assessment for depression and suicide behavior, biochemistry measures, and measurement of the blood level of the CBZ. A physical exam may also be performed at the discretion of the investigator. Full list of assessments can be found on the schedule of events flow sheet.

A Preliminary Study of the Efficacy and Safety of Carbamazepine in Severe Liver Disease Due to Alpha-1 Antitrypsin Deficiency

Assessment of adherence:

Adherence will be assessed at each of the follow up visits by pill counts and patient medication diaries. Medications will only be available from the Investigational Drug Service (IDS), thus an accurate assessment of medication dispensed will be available. Subjects will be instructed to return unused medications at each visit. By pill count, medication adherence will be assessed. Adherence will be defined as intake of > 80% of the prescribed CBZ or placebo – persistent nonadherence to the study regimen may lead to discontinuation of the study for those subjects. For patients receiving CBZ, adherence will also be assessed by measuring trough CBZ levels at each visit. It is expected that the levels will be between 4 and 12 µg/ml. Standard deviations of sequential levels will also be used as a measure of adherence (46).

End of treatment assessment (week 52 visit + 1 wk):

Hepatic venous pressure gradient – see above

Liver biopsy – see above

Concomitant Medications:

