10. ALT > 750 IU/L
 - a. May resume previous dose when ALT < 500
11. Pregnancy
12. Liver transplantation
13. Signs or symptoms of TEN or SJS.
14. Breast feeding.
15. Allergic reaction of Grade 3 or Grade 4.
16. Evidence for behavior or ideation predisposing to suicide (increase in C-SSRS score of 1 from previous test score).

A Preliminary Study of the Efficacy and Safety of Carbamazepine in Severe Liver Disease Due to Alpha-1 Antitrypsin Deficiency

SCREENING AND MANAGEMENT FOR SPECIFIC ADVERSE EVENTS

Patients entering the study will have evidence of chronic liver disease from AT deficiency. At entry into the study, patients may have one or more of the following: elevated serum aminotransferase levels, jaundice, elevated total and direct bilirubin, medically treated ascites, esophageal and/or gastric and/or hemorrhoidal varices, biochemical evidence of hypersplenism with a white blood count (WBC) and platelet count (PLT) below the normal range, and a prolonged prothrombin time (PT) or International Normalized Ratio (INR). Adverse events will be assessed using the Common Terminology Criteria for Adverse Events (CTCAE) Version 4.0. Baseline laboratory values for patients entering the study will likely be above the normal range in the case of ALT, AST, total bilirubin, and INR and below the normal range for hemoglobin, WBC, platelets and neutrophils count. Therefore, changes in laboratory values after initiation of the study drug will need to be assessed within the context of the patient's baseline laboratory tests. We will not be reporting every variation in subject lab results as an adverse event. Small deltas from within normal limits to just outside the normal range are not clinically significant in the care of patients and should not be used to define AEs. The investigative team will use standards that define a minimum delta that determines when a change becomes an AE, either as a discrete value change or a percentage change. These can be used in combination with claims of clinical significance by the site investigator.

An increase of CP score to > 12 , development of Grade III-IV encephalopathy, or total bilirubin > 7 mg/dl will be considered a treatment failure and therapy will be discontinued. Therapy will not be restarted in these subjects even if there is an improvement in clinical status.

Alterations in liver function:

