Objective 1. Determine whether CBZ treatment reduces hepatic ATZ load in AT-deficient patients with severe liver disease.

The primary analysis will test for differences between the treated and placebo groups in the change from baseline to follow-up in the number of hepatocytes with PAS+/diastase-resistant globules using an unpaired t-test (or nonparametric equivalent if appropriate). Given the small sample size, we do not assume that randomization will balance treated and placebo groups at baseline with respect to outcome variables. Therefore, we will compare changes over the course of the treatment rather than differences at the end of the treatment. Secondary analyses will look at the area of a liver section occupied by these globules and the

A Preliminary Study of the Efficacy and Safety of Carbamazepine in Severe Liver Disease Due to Alpha-1 Antitrypsin Deficiency

steady state level of ATZ by immunoblot again using an unpaired t-test (or nonparametric equivalents if appropriate) of the differences between the treated and placebo groups in changes from baseline to follow-up.

Given that the sample is small, randomization may not balance the groups with respect to important covariates, though our ability to detect statistically significant differences is likewise limited to relatively large effect sizes. Furthermore, the number of variables that could be adjusted for in a regression model is also limited by the sample size, as is our ability to do subgroup analyses. However, as exploratory analyses, we will compare the distributions of important confounders between treated and placebo groups and fit multiple linear regression models that include independent variables, in addition to treatment group and baseline values of outcome measures, with variables whose distributions are markedly imbalanced between treatment groups.

Objective 2. Determine whether CBZ treatment reduces hepatic fibrosis in AT-deficient patients with severe liver disease.

Analysis will proceed as in objective 1; however, the outcome will be hepatic fibrosis. The primary analysis will compare treatment group differences in baseline to follow-up changes in hepatic hydroxyproline concentration using an unpaired t-test (or nonparametric equivalent if appropriate). Secondary outcome measures will include Sirius red staining of the liver. Exploratory analyses using multiple regression models will proceed as described above.

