Every effort will be made to ensure adherence by patients, their family and study personnel. This includes inclusion of all eligible patients, accession of initial data in a timely fashion and prompt institution of CBZ treatment. Data sheets will be used to record every step in the protocol including enrollment, collection of initial clinical and lab data, data transmission and initiation of CBZ treatment. Patients will be seen at 4 weeks (+/- 1 week) following initiation of study product and then again at 8 weeks (+/-2 weeks), 18 weeks (+/- 2 weeks), 36 weeks (+/-2 weeks) and finally at the week 52 visit(+3 weeks), which will include the repeat HVPG measurement and liver biopsy.

These visits will involve history, physical exam, pill counts and lab tests to monitor each of the clinical and biochemical parameters mentioned above (refer to Study Flow Chart in Appendix 2). In addition serum levels of CBZ will be measured at each follow- up visit. All data will be recorded on the patient flow log.

OVERALL PATIENT MANAGEMENT

This study will generally not affect patient management, although there will be minor modifications made related to the HVPG measurements. Medications known to influence HVPG measurements (e.g. nonspecific beta blockers) will be discontinued for 3 days prior to HVPG measurements. Each of the subjects is being followed for supportive management of severe liver disease. This will include careful monitoring and medical therapy as indicated by the responsible physician team. At the end of the study period a follow-up HVPG measurement will be performed accompanied by transvenous liver biopsy. As with the first procedure, medications known to influence HVPG measurements will be discontinued for 3 days prior to the procedure. If the subject undergoes liver transplantation during the study period, tissue from the native liver will be collected immediately upon its removal for the analyses proposed above. Follow up HVPG measurements will not be performed in these patients.

PATIENT WITHDRAWAL

It is the right of the patient, the patient's parents or legal guardians, or the physicians caring for the patient to discontinue study medication at any time during the study. Medical care and transplantation will proceed in a manner that is unaffected by study participation.

COMPLETE LIST OF WITHDRAWAL CRITERIA

1. Child-Pugh score >12.
2. Hepatic encephalopathy uncontrolled with outpatient medical therapy.
3. Total bilirubin >7 mg/dl.

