A Preliminary Study of the Efficacy and Safety of Carbamazepine in Severe Liver Disease Due to Alpha-1 Antitrypsin Deficiency

4. Evidence of anticonvulsant hypersensitivity syndrome.
5. Leukocyte count <1,000 despite 2 weeks of CBZ dose reduction.
6. Neutrophil count <500 despite 2 weeks of CBZ dose reduction.
7. Platelet count <20,000 despite 2 weeks of CBZ dose reduction.
8. Hemoglobin <8.5 mg/dl.
9. INR greater than or equal to 2.5 not corrected by vitamin K 5 mg.
10. ALT >750 IU/L.
11. Pregnancy.
12. Breast feeding.
13. Evidence for behavior or ideation predisposing to suicide or increase in C-SSRS score of 1 from previous test score.
14. Persistent non-adherence to medication study regimen.

DATA RETRIEVAL AND STORAGE

A data repository in the University of Pittsburgh computing facility has been established to accept all information about subjects including; demographics, history, physical exam, labs and a tracking/event file. The tracking/event file is designed for important events: study entry; study completion; adverse events; treatment failures; exits; dropouts; protocol violations; etc. Security of the deposited data will be maintained through the use of unique patient identifier numbers and passwords to enter the repository. Data can be exported from the repository for reporting and statistical analysis.

Data quality and accuracy will be audited annually by comparing what is in the database with the medical records of the patients.

The electronic data storage and retrieval system used for the purpose of this clinical investigation has not been fully validated for compliance with the FDA regulations at 21 CFR Part 11 taking into account the limited size and scope of the investigation.

DATA AND SAFETY MONITORING PLAN

The Data and Safety Monitoring Board (DSMB) will consist of individuals who are independent of the institutions and investigators participating in the CBZ study, and who have no financial ties to the outcome of the trial. The ongoing review of the data by this independent committee assures the investigators and the study sponsor that the trial can continue without jeopardizing patient safety. Individuals on the DSMB will be responsible for monitoring data and safety during the course of this study.

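### The plan does not separate stopping study drug from leaving the trial, so subjects withdrawn after randomization can drop out of the biopsy and HVPG comparisons, with bias possible in either direction

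*Combined protocol and SAP*

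**What the plan says.** **Withdrawal.** The complete list of withdrawal criteria has 14 items. They cover worsening liver disease (Child-Pugh, encephalopathy, bilirubin), laboratory toxicity and hypersensitivity (for example "Neutrophil count <500 despite 2 weeks of CBZ dose reduction"), pregnancy and breast feeding, suicidality, and "Persistent non-adherence to medication study regimen".

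**What withdrawal means** varies by section:
- Assessment of adherence: "persistent nonadherence to the study regimen may lead to discontinuation of the study for those subjects".
- On-treatment assessments: "Patients will be withdrawn from the trial if the C-SSRS identifies suicidal ideation or behavior".
- Screening and management for specific adverse events: worsening to set thresholds "will be considered a treatment failure and therapy will be discontinued". This speaks of therapy only.
- Patient withdrawal: opens with the right "to discontinue study medication at any time during the study". This speaks of medication only.
- Indications to discontinue CBZ: repeats 13 of the 14 items (all but non-adherence) and allows drug to be resumed after some of them (WBC, neutrophils, platelets, ALT).

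**Follow-up measurement.** Study Design places the repeat HVPG and biopsy after 12 months of therapy, and they are the content of the end-of-treatment assessment. Early tissue is planned only at transplantation or, with family consent, at autopsy. HVPG is then missing.

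**Analysis.** The primary test is on the "change from baseline to follow-up in the number of hepatocytes with PAS+/diastase-resistant globules using an unpaired t-test", or a nonparametric equivalent. Fibrosis and HVPG follow the same pattern. The document defines no analysis population, no missing-data rule and no sensitivity analysis for missing follow-up.

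**The concern.** A change score needs two measurements. If meeting a withdrawal criterion ends follow-up, the subject has no second biopsy or HVPG and leaves those comparisons. What removes the subject happens after randomization and may depend on the assigned drug or on how the disease is going. The subjects who remain are then no longer the groups that were randomized. Non-adherence stands out because it is not in itself a safety reason to forgo the follow-up measurement.

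Three features could remove more CBZ than placebo subjects:
- CBZ has its own intolerance. In general use, the background Safety section gives 3% discontinuation for side effects and says "Allergic rash occurs in 4 to 10% of patients and is the most common reason for intolerance to CBZ".
- Adherence is judged by pill count and diary in both arms, but also by trough drug level in CBZ subjects only.
- The WBC, neutrophil and platelet criteria require persistence after a CBZ dose reduction. The dose-alteration section says reductions made for reasons other than drug level are not matched on placebo. Read literally, a placebo subject cannot meet these criteria.

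The Child-Pugh, bilirubin and encephalopathy criteria work the other way. If CBZ is effective, they would remove more placebo subjects, and those with worse outcomes.

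A biopsy that was not taken cannot be recovered at the analysis stage.

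**Working it through.** **1. The plan's own power figure.** Inputs from Power calculations: 20 CBZ, 10 placebo, standardized effect d = 1.1, two-sided α = 0.05, stated power 80%.

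Noncentrality = d·√(n₁n₂/(n₁+n₂)) = 1.1·√(200/30) = 2.84 with 28 df. Power is 78.3% by the noncentral t and 81.1% by the normal approximation. The stated figure reproduces, and it assumes that all 30 subjects have follow-up tissue.

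**2. Power if second biopsies are missing.** The documents give no withdrawal rate, so this is an assumed range with equal percentage loss per arm (noncentral t):

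| Missing | CBZ / placebo | Power at d = 1.1 | Effect detectable at 80% |
|---|---|---|---|
| 0% | 20 / 10 | 78.3% | 1.12 |
| 10% | 18 / 9 | 73.6% | 1.19 |
| 20% | 16 / 8 | 68.0% | 1.27 |
| 30% | 14 / 7 | 61.6% | 1.37 |

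The plan's only allowance for loss is 20% for HVPG that cannot be measured. It is described as a loss for the primary aim, but the primary outcome is the globule count, so it does not cover missing biopsies.

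**3. Plausible number lost to CBZ intolerance.** At the 3% discontinuation rate, 20 × 0.03 = 0.6 subjects. Rash at 4% to 10% is 0.8 to 2.0 of 20, but that is incidence, not discontinuation. It overlaps with the 3% and should not be added to it. Both rates describe general use, not cirrhosis. The loss counts below are therefore scenarios, not predictions.

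**4. Bias with no true drug effect.** Assume unit SD, lower is better, and that the k subjects lost in an arm are those worst on a latent score with correlation ρ to the outcome. Let S be the sum of the k largest expected normal order statistics in that arm. Then

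bias (CBZ − placebo) = ρ·[S_P/(10 − k_P) − S_C/(20 − k_C)]; negative favours CBZ.

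The largest expected order statistics are 1.867, 1.408, 1.131 for n = 20 and 1.539, 1.001 for n = 10.

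| Lost CBZ / placebo | Calculation at ρ = 1 | ρ = 0.5 | ρ = 1 |
|---|---|---|---|
| 1 / 0 | −1.867/19 | −0.05 | −0.10 |
| 3 / 0 | −4.406/17 | −0.13 | −0.26 |
| 2 / 1 | 1.539/9 − 3.275/18 | about 0 | −0.01 |
| 1 / 2 | 2.540/8 − 1.867/19 | +0.11 | +0.22 |

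At ρ = 0 every row is zero.

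**5. False-positive rate.** These are simulations of the t-test in the remaining subjects with no drug effect, ρ from 0.5 to 1. The nominal rate is 2.5% in each direction.
- 1 CBZ / 0 placebo lost: significant in favour of CBZ in about 3.4% to 5%.
- 3 / 0 lost: significant in favour of CBZ in about 5% to 13%.
- 2 / 3 lost (10% CBZ, 30% placebo): bias +0.14 to +0.27 SD, significant against CBZ in 5.2% to 12.9%.

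**The case against.** The strongest reply is that the text does not equate stopping drug with leaving the trial. Explicit removal from the trial is stated for C-SSRS findings, and non-adherence only may lead to it. Treatment failure is said to end therapy. The patient-withdrawal section speaks of medication, and the Pregnancy section collects liver outcome after drug is stopped. Overall Patient Management states the end-of-study HVPG and biopsy without requiring the subject to be on drug. Tissue at transplantation and autopsy keeps some of the worst outcomes in the biopsy analyses, and MELD is scored at every visit without a biopsy. This is also a preliminary, resource-limited Phase II study.

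Most of that stands. It shows that the text is ambiguous, not that follow-up is secured, because Study Design ties the repeat procedures to completed therapy. The C-SSRS and non-adherence rules remain as written.

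A reader might infer two stronger things. The first is that the bias favours CBZ. The documents do not support this: the progression criteria apply to placebo as well, no loss rates by arm are given, and 2 CBZ / 1 placebo lost gives almost no bias. Nor does any passage link rash, low counts or missed doses to change in globule count, so ρ is assumed throughout. The second is that the efficacy analysis is completers-only by rule. It is not, given the transplant and autopsy tissue and the unconditional sentence on end-of-study procedures.

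**Conclusion.** The point holds in limited form. The plan has stated rules that can take randomized subjects out after baseline, does not say whether they stay in follow-up, and uses change-score tests that drop anyone without a second measurement. The biopsy and HVPG comparisons can therefore become largely completers-only.

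The possible bias runs from about 0.26 SD in favour of CBZ to 0.22 SD against it in the 3/0 and 1/2 scenarios. It is 0.05 to 0.10 SD in favour of CBZ if a single CBZ subject is lost, and zero if loss is unrelated to outcome. These sizes rest on assumed loss counts and correlations. The power figures rest only on the assumed fraction missing: 78% with none and 68% with 20%. Several arm-specific mechanisms could remove more CBZ subjects, but the net direction cannot be determined from the documents.

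**What to change.** 1. State that meeting a withdrawal criterion, non-adherence included, does not by itself end follow-up. The subject keeps scheduled visits and the already-planned week-52 biopsy and HVPG, unless consent is withdrawn or the physician judges the procedure unsafe.
2. Define the analysis: all randomized subjects with follow-up tissue (or HVPG, for that outcome), in the arm assigned, whatever their adherence or drug status. Pre-specify sensitivity analyses that cover both directions of bias, for example a rank analysis placing treatment failures and deaths worst in both arms.
3. Reconcile the sections on on-treatment assessments, adherence, indications to discontinue CBZ, treatment failure, and patient withdrawal. They must agree on what withdrawal means and on the events that appear both as withdrawal criteria and as events after which drug may be resumed. This changes no rule for stopping drug.

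The cost is protocol and SAP wording, with no new type of procedure. The effect estimate will be somewhat diluted by subjects off drug, and some subjects will decline the second procedure, so the sensitivity analyses are still needed.
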